1.3. OBJECTIVES

Primary Objective: To investigate the safety of Silverlon® dressing in patients throughout their prescribed course of radiation therapy and after radiation therapy.

- Hypothesis: We do not expect any adverse effects from extended use of Silverlon® dressing during and after radiation therapy.
- Primary Outcome Measures: Adverse reactions/events documented by the radiation oncologist as "probable" or "definite" related to Silverlon® Dressing (Weekly AE/Chart Review Source Doc).

Secondary Objective: To evaluate the feasibility of managing radiation dermatitis with Silverlon® dressing.

- Hypothesis: We expect that Silverlon® will be a feasible therapeutic modality for managing radiation dermatitis. We expect high compliance rate during RT and slightly lower when skin symptoms are not presented (i.e., before RT and post-RT). We do not expect any withdrawals due to adverse reactions to the dressing.
- Secondary Outcome Measures: Compliance; Withdrawal rate due to dressing.

Exploratory Objective: To monitor the severity of radiation dermatitis and patient quality of life during use of Silverlon® dressing throughout radiation therapy and after radiation therapy.

• Exploratory Outcome Measures: radiation dermatitis severity (RTOG Score & Radiation Induced Skin Reaction Assessment Scale (RISRAS)); DLQI

Page 7 of 41 RSRB STUDY00004587 Version Date: 09/14/2021 NCT04238728

[figure not shown]

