3. CHARACTERISTICS OF RESEARCH POPULATION

3.1. NUMBER OF SUBJECTS

This is a single site study at the University of Rochester Medical Center, with an accrual goal of 30 fully evaluable subjects. "Fully evaluable" as defined as completing informed consent, meeting eligibility criteria, initiating Silverlon® dressing during radiation therapy and continuing to two weeks after completion of radiation therapy. Therefore, the 30 fully evaluable subjects must complete full protocol procedures. Assuming a 20% withdrawal rate, we will recruit 36 eligible subjects. Subjects who initiated treatment but withdraw from the study will be used in the intent to treat analyses. In the past year, the Wilmot Cancer Institute had 75 patients that would be eligible for this study which demonstrates our ability to reach our accrual goal. To reach this goal of 30 fully evaluable subjects, the total number of subjects approached and/or consented may reach 75 subjects.

PARTICIPANT POPULATION(S)

Accrual Number:	Category/Group: (Adults/Children Special/Vulnerable Populations)	Consented: Maximum Number to be Consented or Reviewed/Collected/ Screened	Intent to Treat: Number to enroll and initiate treatment.	Fully Evaluable: Number to enroll and fully complete study.
Local	75/0/0	75	36	30
Study-wide	75/0/0	75	36	30
Total:	75/0/0	75	36	30

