7. SUBJECT WITHDRAWALS

Subjects will be advised during the consent process that they have the right to withdraw from the study at any time without prejudice or reason. Subjects that withdraw from the study will be replaced with another subject. Subjects will continue to receive radiation therapy as prescribed with standard of care with their treating radiation oncologist. The reason for discontinuation will be recorded in the subject's medical records. The date of occurrence and reasons for any subject withdrawal will be recorded and documented on the **Withdrawal Form**.

Subjects can be withdrawn from the study by the investigator or radiation oncologist for: non-compliance to study procedures; termination of funding; allergic reaction to Silverlon® dressing; worsening of the disease under study; intercurrent illness; pregnancy; or progression of skin reaction to RTOG score ≥3 in the radiation area where the Silverlon® dressing has been applied (i.e., whole breast). RTOG score ≥3 requires patients to have areas moist desquamation outside of skin fold regions (i.e., which would exclude inframammary fold and axillas because these are skin fold regions). Additionally, an area of moist desquamation that is >50% of the radiation treatment area (i.e., RISRAS-HPA score ≥3). Therefore, a large area of moist desquamation outside of skin folds would suggest withdrawal. Pinpoint areas and fold areas of moist desquamation could not require withdrawal. Patients withdrawn from the study will stop using Silverlon® dressing, but continue to receive radiation therapy on their normal schedule as prescribed by the treating radiation oncologist. For patients withdrawn from the study, standard of care for radiation dermatitis will be provided by the treating radiation oncologist, who will continue to follow the patient as per their normal clinical routine. The date of occurrence and reasons for any subject withdrawal will be recorded and documented on the Withdrawal Form. An adverse event will be reported if the skin reaction is RTOG ≥4. This grade of radiation dermatitis is severe and should be reported on the AE Source Doc and following reporting procedures stated in §10. Allergic reaction to Silverlon® dressing will be reported as an unexpected side effect on the AE Source Doc.

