13. DATA ANALYSIS AND MONITORING

13.1. Sample Size Justification

The study will recruit 36 total subjects to accrue 30 fully evaluable subjects with an estimated 20% withdrawal rate. The target enrollment table in §3.9 shows that we have access to enough eligible patients to complete this study in 12 months. The following table shows the

Page 33 of 41 RSRB STUDY00004587 Version Date: 09/14/2021 NCT04238728 precision estimates and 95% confidence intervals for our primary objective (i.e., adverse events related to Silverlon®) and secondary objective (i.e., compliance and withdrawal rate). Our estimates for adverse events (primary and intent to treat analyses) are based on published trials showing no reported adverse events or allergic reactions to silver nylon dressing in patients receiving radiation (8, 15-17). Our estimates for the primary objective were conducted with sample size of 30 for the fully evaluable subjects and 36 for all subjects that initiated treatment. Our estimates for compliance (secondary analyses) are based on the Aquinos-Parsons et al study in breast cancer patients that showed a 97% compliance rate for silver nylon dressing (8). Our estimates for compliance were conducted using sample size of 30 for fully evaluable subjects. In subjects that withdraw from the study, we will be able to partially evaluate compliance because of their early termination of treatment and study procedures. Our estimates for withdrawal are based on the Vavassis et al study in head & neck cancer patients using silver nylon dressing that reported 1 of 12 subjects (i.e., 8%) withdrew from the study (17). Our estimates for withdrawal were conducted using a sample size of 36 to capture all subjects that initiated treatment. 95% Exact Clopper Pearson confidence intervals on the expected proportion have been generated using SAS 9.4.

95% Confidence Intervals								
Objective	Measure	Sample Size	Proportion Estimate	Expected Observed Count	95% LCL	95% UCL		
Primary	# Adverse Events per number of patients	30	0	0	0	0.116		
Intent to Treat	# Adverse Events per number of patients	36	0	0	0	0.097		
Secondary	Compliance	30	0.97	29	0.828	0.999		
Secondary	Withdrawal	36	0.166	6	0.064	0.328		

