13.2. Statistical Analyses

This is a safety study to determine Silverlon® dressing indication for radiation dermatitis. Descriptive statistics will be used to describe the study subject population. The primary analyses will evaluate the number of adverse events or reactions reported (if any) at the breast irradiation site where the Silverlon® dressing was applied. The primary analyses will be conducted on 30 fully evaluable subjects (i.e., 30 subjects that fully complete the study) and on all subjects that initiated treatment with Silverlon® dressing in an intent to treat analysis (see section 13.1). For a safety study, it is important to obtain the overall adverse event rate for all subjects that initiated treatment and all subjects who fully completed the study.

The secondary analyses will evaluate the compliance rates for the Silverlon® Dressing during RT and post RT. Compliance will be on the number of days during RT and post-RT that the dressing was worn. We expect compliance rate to be 97% (8). Additionally, we will evaluate the percentage of subjects that removed the dressing for sleeping. Subjects are asked to wear the dressing during sleep and only remove the dressing for RT sessions, showering/bathing, or swimming. Furthermore, we will calculate the number of hours during a day that the dressing was not worn summing the time between removal and application of the dressing each day.

Page 34 of 41 Version Date: 09/14/2021 Compliance will be evaluated in the 30 fully evaluable subjects. Although we can and will evaluate compliance in all subjects that initiated treatment, these analyses will not provide a complete picture of compliance due to early termination of study procedures. Furthermore, the secondary analyses will also evaluate withdrawal rates due to the Silverlon® dressing in all subjects who initiated treatment. We expect less than 6 subjects to withdraw due to the Silverlon® dressing. The exploratory analyses will assess trends in radiation dermatitis severity (i.e., RTOG and RISRAS) and quality of life (DLQI) during the course of the study. These analyses will also be able to evaluate changes in skin symptoms experience by the patient based on the RISRAS-Patient Symptom Scale during RT.

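### The withdrawal row in section 13.1 shows 6/36, but its cited 8% gives 3/36; and 36 recruits at 20% withdrawal leave 28.8 completers, not 30

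*Combined protocol and SAP*

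**What the plan says.** Section 13.1 opens with the recruitment target: "The study will recruit 36 total subjects to accrue 30 fully evaluable subjects with an estimated 20% withdrawal rate". Section 3.1 says the same, "Assuming a 20% withdrawal rate, we will recruit 36 eligible subjects", and section 3.9 repeats it.

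For the precision of the withdrawal rate, section 13.1 gives as its source a head and neck study "using silver nylon dressing that reported 1 of 12 subjects (i.e., 8%) withdrew from the study". It gives the denominator too: "Our estimates for withdrawal were conducted using a sample size of 36 to capture all subjects that initiated treatment". The table row marked Secondary / Withdrawal then shows n = 36, proportion 0.166, expected count 6, and 95% limits 0.064 and 0.328. The intervals are stated to be exact Clopper-Pearson.

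Section 1.3 defines the outcome: "Secondary Outcome Measures: Compliance; Withdrawal rate due to dressing". Section 13.2 says "the secondary analyses will also evaluate withdrawal rates due to the Silverlon® dressing in all subjects who initiated treatment", and adds "We expect less than 6 subjects to withdraw due to the Silverlon® dressing". Section 7 provides that "Subjects that withdraw from the study will be replaced with another subject", and sections 3.1 and 3.9 allow up to 75 subjects to be approached or consented.

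**The concern.** Section 13.1 carries three withdrawal figures that are not reconciled: 20% for recruitment, 8% as the cited basis for precision, and 0.166 in the table.

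The table row does not follow from the source named for it. It is also unclear what it measures. Its Secondary label points to withdrawal due to the dressing, but a count of 6 is not below 6, as section 13.2 expects for that outcome. Read as withdrawal for any cause, a count of 6 is possible, but then the row is not the precision of the secondary outcome.

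The 20% rate does not turn 36 recruits into 30 completers.

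Withdrawal due to the dressing is one of only two secondary outcome measures, and this table is the plan's whole precision justification. The results are meant to support a 510(k) application, so a reader should be able to trace each planning figure to its stated source. If recruitment runs at the stated 20%, the number initiating treatment would also be expected to pass 36, the denominator fixed in the table for the intent-to-treat and withdrawal intervals.

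**Working it through.** **Inputs.** 36 recruited, 30 fully evaluable and 20% withdrawal (sections 3.1, 3.9, 13.1); 1 of 12 withdrew (section 13.1 text); withdrawal row 0.166, count 6, limits 0.064 and 0.328 (section 13.1 table); fewer than 6 dressing-related withdrawals expected (section 13.2); withdrawals replaced (section 7).

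**Method.** For x events in n, the two-sided 95% Clopper-Pearson limits are the beta quantiles: lower = Beta(0.025; x, n − x + 1), upper = Beta(0.975; x + 1, n − x), with lower = 0 when x = 0.

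**Step 1: reproduce the table.**

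| Row | x/n | Computed limits | Printed limits |
|---|---|---|---|
| Adverse events, evaluable | 0/30 | 0 to 0.1157 | 0 to 0.116 |
| Adverse events, intent to treat | 0/36 | 0 to 0.0974 | 0 to 0.097 |
| Compliance | 29/30 | 0.8278 to 0.9992 | 0.828 to 0.999 |
| Withdrawal | 6/36 | 0.0637 to 0.3281 | 0.064 to 0.328 |

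All four intervals are right for the counts printed. The first three counts also follow from their stated basis: no adverse events, and 97% compliance (29/30 = 0.967).

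**Step 2: withdrawal row from its stated basis.** 36 × 1/12 = 3.0 (36 × 0.08 = 2.88, which also rounds to 3). 3/36 = 0.083, limits 0.0175 to 0.2247. The printed count is 6, a proportion of 6/36 = 0.1667. The interval widths are 0.328 − 0.064 = 0.264 as printed and 0.225 − 0.018 = 0.207 on the cited basis.

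A count of 6 equals 36 − 30, the recruitment allowance. That may be where it came from, but the plan does not say so.

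**Step 3: withdrawal row as the dressing-related outcome.** The largest count below 6 is 5. 5/36 = 0.139, limits 0.047 to 0.295.

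**Step 4: recruitment.**
- 30 × 1.20 = 36, so the printed 36 adds 20% of the completers instead of allowing for a loss of 20% of recruits.
- 36 × 0.80 = 28.8 expected completers, a shortfall of 1.2.
- 30/(1 − 0.20) = 37.5, so 38 recruits, two more than planned.
- 1 − 30/36 = 16.7% is the rate at which 36 yields 30.
- Without replacement, and with independent withdrawals at 20%, the binomial probability of at least 30 completers is 0.40 from 36 recruits and 0.66 from 38.

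**Step 5: effect of replacement.** Suppose recruitment continues until 30 complete and withdrawals are independent. The number initiating treatment is then negative binomial with mean 30/(1 − rate). At 20% the mean is 37.5, with a central 95% range of 32 to 44. At 16.7% the mean is 36.0, with a range of 31 to 42. The zero-event upper limit is 1 − 0.025^(1/n): 0.109 at n = 32, 0.097 at n = 36 and 0.080 at n = 44.

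**The case against.** The strongest reply is that little depends on either slip. Replacement and the ceiling of 75 mean that 30 completers can be reached whatever rate is written down. The recruitment gap is two subjects, there is no power calculation to disturb, and no success criterion or stopping rule uses the withdrawal row. The final interval will come from observed data. This stands, and it limits the weight of the point. Replacement does not, however, repair a table row that disagrees with its own source.

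A second reply is that 6 is the allowance for withdrawal from any cause. Dressing-related withdrawals are a subset of these, so a total of 6 is compatible with fewer than 6 due to the dressing. That is a fair reading, and on it the conflict with section 13.2 disappears. But the row then needs that label, the 8% is not its source, and the secondary outcome has no precision figure.

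A third reply is that the wider interval is merely cautious, and that 1 of 12 is itself so imprecise (exact limits 0.002 to 0.385) that 17% is compatible with it. Both are true, but the text offers neither as its reason. It names 8% as the basis.

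Finally, 16.7% is worked back from 36 and 30 and has no outside support, so keeping 20% and recruiting 38 is an equally valid repair. That is correct. The fix below gives it as an alternative.

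**Conclusion.** The concern holds on both counts. The withdrawal row shows 6/36 (0.064 to 0.328), whereas its stated basis gives 3/36 (0.018 to 0.225), and it does not say which kind of withdrawal it measures. The 20% rate gives 28.8 completers from 36 recruits; 36 fits a rate of 16.7%, and 20% needs 38.

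The withdrawal row is the more important half, because it leaves a secondary outcome with a precision figure that cannot be traced. The recruitment half is a small inflation slip. Neither affects the evaluable target, the adverse event or compliance intervals at their stated n, or the analyses.

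The mismatches in the row and in the recruitment figures are plain arithmetic and need no assumptions. The conflict with section 13.2 depends on reading the row as dressing-related. The completion probabilities and the ranges for the number initiating treatment assume independent withdrawals, and the ranges also assume recruitment until exactly 30 complete.

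**What to change.** 1. In sections 3.1, 3.9 and 13.1, keep 36 and replace 20% with 16.7% (6/36). Alternatively, keep 20%, state 38 recruits, and update the participant table in section 3.1 and the n = 36 rows in section 13.1.
2. In the section 13.1 table, make the withdrawal row match its basis. Either label 6/36 (0.064 to 0.328) as the allowance for withdrawal from any cause and drop the 8% study as its source, or print 0.083, count 3, limits 0.018 to 0.225.
3. State whether the row is withdrawal for any cause or withdrawal due to the dressing. If the latter, give a count that fits the section 13.2 expectation (at most 5/36, 0.047 to 0.295) together with its reason. Section 1.3 expects no withdrawals from adverse reactions to the dressing, and any count chosen should be squared with that. Section 13.1 gives no cause for the 1 of 12 withdrawal, so the 8% should not be presented as a dressing-related rate.
4. Add a sentence that, because withdrawals are replaced, the number initiating treatment may exceed the planned figure, and that the intent-to-treat and withdrawal intervals will use the actual number.

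With 36 kept, the cost is wording in three places, one table row and one added sentence, with no added patients and no change to the analyses. The alternative adds two recruits to the planned number.

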10. SAFETY AND REPORTABLE EVENTS

10.1. ADVERSE EVENT MONITORING

This is a safety study to determine if Silverlon® dressing can be indicated for radiation dermatitis. The primary outcome is not clinical response to treatment; it is safety (i.e., adverse reactions/events/complications). Any adverse event will be documented on the AE Source Doc throughout the course of the study. Any safety information for an individual patient that is volunteered by a study subject during the course of this research must be reported as described below:

All adverse events, whether observed by the Investigator radiation oncologist, or nurse, elicited from, or volunteered by the subject, will be documented. Each adverse event will be recorded on the electronic AE Source Doc. This form will record the will include a brief description of the experience, the date of onset, the date of resolution, the duration and type of experience, the severity, contributing factors, and any actions taken. This description will be in the summary not during a subject's regularly scheduled clinic appointment.

Adverse event (AE): is any untoward medical occurrence in a subject using study device, and which does not necessarily have a causal relationship with this treatment. An adverse event can be any unfavorable and unintended sign (including abnormal laboratory test results), symptom, or disease temporally associated with the use of the study device, whether or not considered related to the study device. The relationship of each adverse event to the study device must be recorded as one of the choices on the scale described below.

Attribution: An assessment of the relationship between the adverse event and the protocol treatment, using the following categories.

ATTRIBUTION	DESCRIPTION
Unrelated	The AE is clearly NOT related to treatment.
Unlikely	The AE is doubtfully related to treatment.
Possible	The AE may be related to treatment.
Probable	The AE is likely related to treatment.
Definite	The AE is clearly related to treatment

Page 30 of 41 RSRB STUDY00004587 Version Date: 09/14/2021 NCT04238728 **Hospitalization (or prolongation of hospitalization):** For AE reporting purposes, a hospitalization is defined as an inpatient hospital stay equal to or greater than 24 hours. **Life Threatening Adverse Event:** Any AE that places the subject at immediate risk of death from the AE as it occurred.

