11. DATA AND SAFETY MONITORING PLAN

[name] (co-investigator) in Radiation Oncology at University of Rochester will serve as the Clinical Monitor for this study. Approval of protocol, informed consent

Page 32 of 41 RSRB STUDY00004587 Version Date: 09/14/2021 NCT04238728 procedures, and recruitment will be obtained from the University RSRB. Any safety concerns about the clinical protocol will be brought to the immediate attention of the Principal Investigator and Co-investigator. Study personnel will follow aforementioned reporting procedures for adverse event reporting, including any serious adverse events. Protocol deviations and quality issues will be recorded and reported to the IRB per local policies. Remedial and/or corrective action to prevent reoccurrence of protocol deviations or quality issues will be instituted as necessary. Because this study's procedures pose relatively low risk to subjects, monthly data and procedural reviews by the Clinical Monitor and Investigator in consultation with study personnel will be sufficient to identify and ameliorate any potential safety issues. As such, an additional Data and Safety Monitoring Plan document will be not be created for this study.

Patients will have their radiated sites examined once a week by either a radiation oncologist as part of their regular course of radiation therapy. At this examination, any adverse events related to their skin will be recorded. For the purpose of this study, an adverse event will be defined as severe radiation dermatitis meeting the definition of RTOG score grade 4 or above (ulceration, hemorrhage or necrosis) or other adverse reaction of Grade 3 or higher in the area of radiation area where Silverlon® dressing is applied. Patients meeting the definition of 'adverse event' will be withdrawn from the study and the radiation dermatitis then treated according to local protocol as ordered by the attending radiation oncologist. Changes in dose or scheduling of radiation therapy in response to an adverse event will remain the responsibility of the attending radiation oncologist.

If a patient feels that they are having an adverse event outside of the weekly monitoring schedule, they may contact the study coordinator or principal investigator by phone and an immediate follow-up appointment with the radiation oncologist will be arranged.

12. STUDY MONITORING PLAN – Sponsor

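### The primary safety measure is an adverse event count with a subject-level interval; section 11's narrower AE definition and the completer set both favour zero, and compliance has no rule linking days worn to compliant subjects

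*Combined protocol and SAP*

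**What the plan says.** **Primary measure.** Section 1.3 gives the primary outcome as "Adverse reactions/events documented by the radiation oncologist as" probably or definitely related to the dressing. It sets no grade limit and no site limit. Section 13.2 says the primary analyses will "evaluate the number of adverse events or reactions reported (if any) at the breast irradiation site", and later speaks of an overall AE rate. The section 13.1 table heads both AE rows "Adverse Events per number of patients", with 0 expected in 30 (labelled Primary) and 0 in 36 (labelled Intent to Treat). The method is given as: "95% Exact Clopper Pearson confidence intervals on the expected proportion have been generated using SAS 9.4".

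**What an AE is.** Under section 10.1 an AE "is any untoward medical occurrence in a subject using study device, and which does not necessarily have a causal relationship with this treatment", and each one is recorded with an attribution. Section 11 says that, for this study, "an adverse event will be defined as severe radiation dermatitis meeting the definition of RTOG score grade 4 or above", or another reaction of Grade 3 or higher where the dressing is applied. Subjects who meet that definition are withdrawn.

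**Analysis sets.** Section 13.2 plans the primary analysis in the fully evaluable subjects and in all who started treatment. Section 3.1 states: "Therefore, the 30 fully evaluable subjects must complete full protocol procedures". Section 7 replaces subjects who withdraw.

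**Compliance.** Section 13.2 bases compliance on the number of days the dressing was worn and expects 97%. The 13.1 row is n=30, proportion 0.97, count 29, limits 0.828 to 0.999.

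**The concern.** A Clopper-Pearson interval needs one yes/no result per subject. An event count over patients is a different quantity: one subject can contribute several events, and with more events than patients the binomial interval does not exist. Repeat events are possible here, because every AE is recorded separately, the form is completed weekly, and a mild related reaction does not meet section 11's definition and so does not lead to withdrawal under it.

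The larger problem is that the plan does not settle which events enter the count. The composite data are intended for a 510(k) submission (section 14) and the expected result is zero. If the choice between the section 1.3 and section 11 definitions is left until data are in hand, that choice could decide whether zero is reported. The set labelled Primary is also conditioned on finishing the protocol, which a subject withdrawn for an AE does not do.

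For compliance, the stated precision belongs to a measure that section 13.2 does not define.

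**Working it through.** **1. Reproducing the printed table** (inputs: n and counts from 13.1; two-sided 95%).

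With 0 events the Clopper-Pearson upper limit is 1 − 0.025^(1/n). Otherwise the limits are beta quantiles: lower B(0.025; x, n−x+1), upper B(0.975; x+1, n−x).

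- 0/30: upper 0.1157 (printed 0.116)
- 0/36: upper 0.0974 (printed 0.097)
- 29/30: 0.8278 to 0.9992 (printed 0.828 to 0.999)
- 6/36: 0.0637 to 0.3281 (printed 0.064 to 0.328)

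All four rows agree, so every row treats the subject as the unit.

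**2. Count against proportion at zero events.** If events per patient were really meant, and events were independent, the exact Poisson upper limit would be −ln(0.025)/n = 3.689/n: 0.1230 for n=30 and 0.1025 for n=36. The gaps from the printed limits are about 0.7 and 0.5 percentage points.

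**3. Count against proportion when events recur** (illustration, not from the documents: 3 of 36 subjects with 2 events each).

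| Reading | Estimate | 95% limits |
|---|---|---|
| Subjects with at least one event, 3/36 | 8.3% | 1.8 to 22.5% |
| Count entered as binomial, 6/36 | 16.7% | 6.4 to 32.8% |
| Exact Poisson, 6 events in 36 | 0.167 per patient | 0.061 to 0.363 |

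The Poisson row is for comparison only. In this pattern the per-subject variance is 3×4/36 − (6/36)² = 0.333 − 0.028 = 0.31, against a mean of 0.17, so independence fails and that interval is too narrow.

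**4. Effect of the definition** (illustration: 3 of 36 treated subjects have a mild reaction rated probable, and there are no other events).

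- Section 1.3: 3/36 = 8.3% (1.8 to 22.5%)
- Section 11: 0/36 (0 to 9.7%)

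**5. Effect of the analysis set** (illustration: 36 start; 6 withdraw, 3 of them because they met section 11's definition during wear; none of the 30 completers has an event).

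- All treated: 3/36 (1.8 to 22.5%)
- Fully evaluable: 0/30 (0 to 11.6%)

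**6. Compliance.** 0.97 × 30 = 29.1, which rounds to the printed 29. To show that days worn do not determine this count, take the shortest course in section 3.5: 15 fractions. Assuming 5 per week from a Monday without breaks, that is 19 days, plus 14 after RT = 33 wear days. Let 6 of 30 subjects miss 5 days each and the others none: (990 − 30)/990 = 97.0% of days worn. Each of the 6 has worn it on 28/33 = 84.8% of days.

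- Cut-off 80% of days: 30/30 compliant (88.4 to 100%)
- Cut-off 90% of days: 24/30 compliant (61.4 to 92.3%)
- Printed row: 29/30 (82.8 to 99.9%)

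If compliance is instead the mean share of days worn, the limits are 0.97 ± t × SD/√30. The SD is not given. Assumed values of 0.03, 0.05 and 0.10 give 0.959 to 0.981, 0.951 to 0.989, and 0.933 to 1 (capped). None of these resembles the printed row.

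**The case against.** Section 13.1 heads the column as a proportion estimate and describes the intervals as being on a proportion, so a per-subject measure was probably intended. That is fair. At zero events the two readings nearly coincide, and the unit point alone would be a wording correction. A reader might go further and infer that the printed limits are wrong or the sample size inadequate. Neither follows: the limits are correct for subjects and nothing in the sample size changes.

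A reader might also infer a four-way contradiction among sections 1.3, 7, 10.1 and 11. The documents do not support that. Section 10.1 says what is collected and requires attribution, and 1.3 selects the probable and definite events, which is an ordinary subset. The section 7 sentence, "An adverse event will be reported if the skin reaction is RTOG ≥4", concerns radiation dermatitis, and the same paragraph sends allergic reactions to the AE form without a grade threshold. Section 11 is the real conflict, because it redefines an AE for the study as a whole.

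It is also tempting to say that the n=30 set cannot contain an event meeting section 11's definition. That is too strong: one first found at the 2-week post-RT visit or later can occur in a subject who has completed wear. Finally, section 13.2 already plans the all-treated analysis, so what is missing is its priority.

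**Conclusion.** The concern holds in this form. The stated primary measure is a count, while its stated precision is that of a proportion of subjects. The difference is 0.5 to 0.7 points at zero events and becomes material only if events recur within subjects.

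The definition conflict weighs more. The same data could be reported as 3/36 or 0/36 depending on whether section 1.3 or section 11 is followed, and the n=30 set labelled Primary is selected towards zero because section 11 withdraws most of the subjects whose events it counts. For compliance, no rule connects days worn with the 29/30 row. The documents do not show whether the cited 97% was per subject or per day.

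The limits in the illustrations are exact for the patterns shown. The event patterns, compliance cut-offs, SDs and five-fractions-per-week schedule are assumptions.

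**What to change.** 1. In sections 13.1 and 13.2, state the primary measure as the number and proportion of subjects with at least one AE rated probable or definite (the section 1.3 outcome), with Clopper-Pearson limits. List event counts separately. The printed zero-event limits can stay.
2. Reconcile section 11 with sections 1.3 and 10.1 so that one definition feeds the primary count. Also reconcile the site restriction in section 13.2 and on the AE form (section 5.3) with section 1.3, which has none. Otherwise the systemic allergic reactions foreseen in section 9.1 could be left out even when judged related. Withdrawal rules remain for the study team.
3. Make the all-treated set the lead safety result and the fully evaluable set supportive.
4. For compliance, choose one of two routes before analysis. Either report the mean share of scheduled days worn with its interval, or pre-specify a per-subject cut-off and restate the assumed proportion and limits in the 13.1 row. The present 29/30 should not be carried over to a cut-off without support. Either route needs a definition of a day worn, since the log described in section 5.4 records hours.

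The cost is wording and minor programming, with no new data and no change in sample size. The downside is that the lead safety and compliance figures may look less favourable.
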